9 STUDY POPULATION

Eligibility will be reviewed and documented by an appropriately qualified member of the investigator's team before subjects are enrolled.

9.1 Inclusion Criteria

Part A and Part B

Subjects who meet all of the following inclusion criteria will be eligible.

- 1. Subject's legally appointed and authorized representative (e.g., parent or legal guardian) will sign and date an ICF and the subject will sign and date an assent form (if applicable).
- 2. Subject's legally appointed and authorized representative (e.g., parent or legal guardian) is willing and able to comply with scheduled visits, treatment plan, study restrictions, laboratory tests, and other study procedures.
- 3. Subjects (males and females) will be between 2 and 5 years of age, inclusive, on the date of informed consent (and assent, if applicable) for the relevant study part.
- 4. Subjects who weigh ≥8 kg without shoes and wearing light clothing at the Screening Visit.
- 5. Subjects with confirmed diagnosis of CF³⁶ at the Screening Visit. CF is defined as:
 - 2 CF-causing mutations (all as documented in the subject's medical record) AND
 - ullet chronic sinopulmonary disease \underline{OR} gastrointestinal/nutritional abnormalities; \underline{OR}
 - Part B only: a sweat chloride value ≥60 mmol/L by quantitative pilocarpine iontophoresis as documented in the subject's medical record OR from the sweat chloride test result obtained at the Screening Visit. If an eligible historical sweat chloride result is documented in the subject's medical record, that result alone [and not the Screening Visit result] may be used to determine eligibility.

- 6. Subjects who are homozygous for *F508del* (genotype to be confirmed at the Screening Visit). If the *CFTR* screening genotype result is not received before Day -1, a previous *CFTR* genotype laboratory report may be used to establish eligibility. Note:
 - Subjects who have been enrolled and whose screening genotype does not confirm study eligibility must be discontinued from the study, as described in Section 9.5.
 - This assessment does not need to be repeated for confirmed subjects in Part A who may participate in Part B.
- 7. Subjects with stable CF disease as deemed by the investigator at the Screening Visit.
- 8. Subjects who are willing to remain on a stable CF medication regimen through Day 15 (Part A) or through the Safety Follow-up Visit (Part B), if applicable.

9.2 Exclusion Criteria

Part A and Part B

Subjects who meet any of the following exclusion criteria will **not** be eligible.

- 1. History of any comorbidity reviewed at the Screening Visit that, in the opinion of the investigator, might confound the results of the study or pose an additional risk in administering LUM/IVA to the subject. For example, a history of cirrhosis with portal hypertension.
- 2. Any clinically significant laboratory abnormalities at the Screening Visit that would interfere with the study assessments or pose an undue risk for the subject (as deemed by the investigator).
- 3. Any of the following abnormal laboratory values at the Screening Visit:
 - Hemoglobin <10 g/dL
 - Alanine aminotransferase (ALT), aspartate aminotransferase (AST), or total bilirubin >2 × upper limit of normal (ULN)
 - Abnormal renal function defined as glomerular filtration rate ≤45 mL/min/1.73 m² (calculated by the Bedside Schwartz equation)³⁷
- 4. An acute upper or lower respiratory infection, pulmonary exacerbation, or changes in therapy (including antibiotics) for pulmonary disease within 28 days before Day 1 (first dose of LUM/IVA).
- 5. A standard 12-lead ECG demonstrating QTc >450 msec at the Screening Visit. If QTc exceeds 450 msec at the Screening Visit, the ECG should be repeated 2 more times during the Screening Period, and the average of the 3 QTc values should be used to determine the subject's eligibility.
- 6. History of solid organ or hematological transplantation.

- 7. Ongoing or prior participation in an investigational drug study (including studies investigating LUM and/or IVA) within 30 days of the Screening Visit.
 - A washout period of 5 terminal half-lives of the previous investigational study drug, or 30 days, whichever is longer, must elapse before the Screening Visit.
 - The duration of the elapsed time may be longer if required by local regulations. Note: Ongoing participation in a noninterventional study (including observational studies) is permitted.
- 8. Use of restricted medication or food within specified duration before the first dose of LUM/IVA as defined in Section 9.3.
- 9. History of cataract/lens opacity or evidence of cataract/lens opacity determined to be clinically significant by a licensed ophthalmologist during the ophthalmologic examination at the Screening Visit. The Screening Visit ophthalmologic examination does not need to be repeated if there is documentation of an examination meeting protocol criteria that was conducted within 3 months before the Screening Visit (Section 11.6.6). Subjects with documentation of bilateral lens removal do not need the ophthalmologic examination and this criterion does not apply.
- 10. The subject or a close relative of the subject is the investigator or a subinvestigator, research assistant, pharmacist, study coordinator, or other staff directly involved with the conduct of the study.

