LUM/IVA will be administered q12h (± 1 hour), approximately 30 minutes from the start of consuming fat containing food such as a standard "CF" high fat, high calorie meal or snack according to the guidelines in Section 10.2.1. The morning dose on Day 15 is the last dose of LUM/IVA.

Table 3-3 Study VX15-809-115: Part B Screening

Assessment	Screening Visit Day -28 through Day -1
Informed consent/assent	X
Demographics	X
Medical and ophthalmological history	X
Stature, weight, and vital signs ^{a,b}	X
Pulse oximetry ^b	X
Ophthalmologic examination ^c	X
Full physical examination	X
Standard 12-lead ECG ^d	X
CFTR genotype ^e	X
Serum chemistry ^f	X
Hematology ^f	X
Coagulation studies ^f	X
Urinalysis ^f	X
Sweat chloride ^g	X
LCI (optional) ^h	X
Spirometry ⁱ	X
Medications review ^j	Continuous from signing of ICF through Safety Follow-up Visit (if required)
Adverse events	Continuous from signing of ICF through Safety Follow-up Visit (if required)

BMI: body mass index; CFTR: cystic fibrosis transmembrane conductance regulator gene; ECG: electrocardiogram; ICF: informed consent form; LCI: lung clearance index

- ^a If children can stand unassisted and follow directions, stature should be measured as height; otherwise, stature will be measured as length. Stature and weight must be measured with shoes off and while wearing light clothing. BMI will be derived from this assessment. Refer to Section 11.4.3 for details.
- The subject should rest for at least 5 minutes before having vital signs and pulse oximetry measured. Refer to Section 11.6.4 for details.
- An ophthalmologic examination will be conducted by a licensed ophthalmologist. The examination does not need to be repeated if there is documentation of an examination meeting protocol criteria that was conducted within 3 months before the Screening Visit. Subjects with documentation of bilateral lens removal do not need the ophthalmologic examination. Refer to Section 11.6.6 for details.
- A standard 12-lead ECG will be performed. The subject will be instructed to rest in the supine position for at least 5 minutes, if possible, before having an ECG performed. The ECG will be performed before any other procedures that may affect heart rate, such as blood draws. Refer to Section 11.6.5 for details.

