8 STUDY DESIGN

8.1 Overview of Study Design

This is a Phase 3, 2-part, open-label, multicenter study evaluating the PK, safety, tolerability, and PD of multiple doses of LUM/IVA in subjects 2 through 5 years of age (inclusive) with CF, homozygous for *F508del*. Subjects who participate in Part A may participate in Part B, if they meet the eligibility criteria.

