8.3.3 Rationale for Study Assessments

The safety and PK assessments are standard parameters for clinical studies in drug development and are generally recognized as reliable, accurate, and relevant to the study of subjects with CF. Ophthalmologic examinations and spirometry assessments were added to the standard safety assessments. In addition, assessments were added to evaluate the PD effects of LUM/IVA and the acceptability/palatability of LUM/IVA granules.

Ophthalmologic Examinations: A juvenile rat toxicity study performed to support dosing of IVA in subjects <2 years of age demonstrated lens opacities in some animals. Prior studies in rats and dogs of older age did not demonstrate similar findings. Given substantial differences between human and rat lens development, the finding is of unlikely relevance to humans. Periodic ophthalmologic examinations for pediatric subjects receiving IVA or IVA in combination with a CFTR corrector are being performed to confirm this interpretation. The overall data acquired to-date does not suggest an association between IVA treatment and cataract development; however, a potential association has not been fully excluded.

Spirometry: Spirometry is included as part of standard safety monitoring. Because the quantitative assessment of pulmonary function in young children is difficult, the spirometry testing will only be performed on subjects who are ≥ 3 years of age at screening. Even with this age stipulation, it is anticipated that reproducible spirometry will be obtained in a minority of the study population.

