11.6.6 Ophthalmologic Examination

Part A and Part B

In Part A, subjects will undergo an ophthalmologic examination at the Screening Visit (Table 3-1).

In Part B, subjects will undergo an ophthalmologic examination at the Screening Visit (Table 3-3) and at the Week 24 Visit OR the ETT Visit OR the Safety Follow-up Visit, as applicable (Table 3-4).

The ophthalmologic examination includes:

- measurement of best corrected distance visual acuity of each eye
- pharmacologically dilated examination of the lens with a slit lamp

These examinations must be conducted by a licensed ophthalmologist. The Part A and Part B screening ophthalmologic examination must be completed and the results reviewed before enrollment. If cataract/lens opacity is identified and determined to be clinically significant by the licensed ophthalmologist at the screening examination, the subject must not be enrolled. The screening ophthalmologic examination does not need to be repeated if there is documentation of an examination meeting protocol criteria that was conducted within 3 months before the Screening Visit. Subjects with documentation of bilateral lens removal do not need the ophthalmologic examination.

If a cataract or lens opacity is identified and determined to be clinically significant by a licensed ophthalmologist after dosing, the subject/caregiver will be notified. After discussion with the site principal investigator and in collaboration with the Vertex medical monitor, the subject/caregiver may elect to continue or discontinue LUM/IVA. If the subject discontinues LUM/IVA, the subject will be asked to remain in the study and complete the study assessments as noted in Section 8.1.10. If the subject continues, more frequent ophthalmologic monitoring should be considered.

In addition, at the Screening Visit, the following history will be obtained for all subjects:

- history of steroid use
- history of trauma to the eye
- any family history of glaucoma, congenital cataracts, or cataracts arising later in life

Additional ophthalmologic examinations may be conducted at the discretion of the investigator. The Vertex medical monitor or designee should be notified of any additional ophthalmologic examinations.

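### The 3-month waiver lets an eye examination done before Part A dosing serve as the Part B screening examination for a child already given LUM/IVA

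*Protocol*

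**What the plan says.** The waiver appears in three places that govern Part B entry. Criterion 9 in Section 9.2 says of the screening examination that it "does not need to be repeated if there is documentation of an examination meeting protocol criteria that was conducted within 3 months before the Screening" (meaning the visit). The footnote to Table 3-3 repeats it: "The examination does not need to be repeated if there is documentation of an examination meeting protocol criteria", with the same 3-month limit. Section 11.6.6 applies it to both parts and adds "The Part A and Part B screening ophthalmologic examination must be completed and the results reviewed before enrollment". Section 8.1.5 carries a matching 3-month exemption for rescreening. None of these sets a condition on drug exposure between the examination and Part B.

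For Part A, Section 11.6.6 says "In Part A, subjects will undergo an ophthalmologic examination at the Screening Visit (Table 3-1"). Table 3-2, which covers Part A treatment and follow-up, has no eye-examination row. In Part B the next required examination after screening is at Week 24, the early termination visit or the Safety Follow-up Visit (Table 3-4).

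Movement between the parts is allowed: "Subjects who participate in Part A may participate in Part B, if they meet the eligibility criteria" (Section 8.1). Criterion 7 excludes "Ongoing or prior participation in an investigational drug study (including studies investigating LUM and/or IVA) within 30 days of the Screening Visit", and its first sub-item makes the gap 30 days or five half-lives of the earlier drug, whichever is longer. The protocol does not say whether Part A counts as an earlier study.

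Section 8.3.3 explains the examinations: for IVA and cataract, "a potential association has not been fully excluded". Section 7.1 names ophthalmological examinations in the Part B primary safety endpoint.

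**The concern.** The Part B screening examination has two uses. It applies criterion 9, which is meant to stop a child with a clinically significant opacity from being enrolled, and it is the lens baseline against which the end-of-treatment examination is read. Both uses need it to describe the lens as it is when Part B begins.

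For a child coming from Part A, the waiver can break that link. The Part A screening examination is one that meets protocol criteria, and it predates about 15 days of LUM/IVA. If it is carried forward, the first required look at the lens after any exposure comes at the end of Part B. An opacity that developed in Part A would not be caught at Part B entry, and at Week 24 nothing on record would show which part it belonged to. The history limb of criterion 9 does not help, because an opacity nobody has looked for has no history.

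The protocol does provide for children who move between parts on another item: criterion 6 and the Table 3-3 footnotes say their genotype need not be repeated. It has no corresponding rule for the eyes.

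**Working it through.** **Inputs.** Part A screening Day -28 to Day -1, last dose Day 15 (± 2 days), follow-up 10 ± 3 days after the last dose (synopsis, Table 3-2). Screening may be extended by 1 week (Section 8.1.6). Waiver limit 3 months, which is 89 to 92 days by calendar. Gap of 30 days under criterion 7. About 12 subjects in Part A and 56 in Part B (Section 8.1).

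**The plan's own figure.** Part A duration: 28 + 15 + 10 = 53 days, as the synopsis states.

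**Age of the examination at the Part B Screening Visit.** There is no Day 0, so Day 15 is 14 days after Day 1 and Day -k is k days before it. For an examination on Day -k and a Part B Screening Visit g days after the last dose, age = 14 + g + k.

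| Reading of criterion 7 | g | Exam on Day -1 | Exam on Day -28 |
|---|---|---|---|
| 30 days from last dose | 30 | 14 + 30 + 1 = 45 | 14 + 30 + 28 = 72 |
| 30 days from the follow-up visit | 10 + 30 = 40 | 14 + 40 + 1 = 55 | 14 + 40 + 28 = 82 |
| Part A not counted; screening at the follow-up visit | 10 | 14 + 10 + 1 = 25 | 14 + 10 + 28 = 52 |

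Every entry is below 89 days. With criterion 7 applied, the range is 45 to 82 days.

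**Late edges.** Last dose on Day 17 (16 days after Day 1), follow-up at +13 days, then 30 days, with an examination on Day -28: 16 + 13 + 30 + 28 = 87 days, still inside. Extended screening (Day -35) with every late edge: 16 + 43 + 35 = 94 days, outside.

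**When the waiver lapses.** Taking 3 months as 90 days, the latest valid Part B Screening Visit is 90 - 14 - k days after the last dose: 75 days for an examination on Day -1 and 48 days for one on Day -28. With 89 or 92 days instead, these become 74 and 47, or 77 and 50.

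**Five half-lives.** The protocol gives no half-life, so 30 days is assumed to be the longer limb of criterion 7. Counted from the last dose, the five-half-life limb would close the window only for a half-life above 48/5 = 9.6 days (examination on Day -28) or 75/5 = 15 days (examination on Day -1).

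**Ceiling on numbers.** If all 12 Part A children moved to Part B and all used the waiver: 12/56 = 21%.

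**The case against.** The strongest objection concerns reach. The protocol gives no timetable from Part A to Part B. Part B doses follow an internal review of safety, tolerability and PK data, further Part A subjects or cohorts may be added first, and the IDMC charter must be final before the first Part B enrolment. If these steps take longer than about 48 to 75 days after a child's last dose, the waiver has lapsed for that child. Children dosed early in Part A are least likely to qualify. A Part A examination may itself have been accepted from up to 3 months before Part A screening, and could then be too old. The waiver is also optional, and Section 11.6.6 allows extra examinations at the investigator's discretion. All of this stands. It means that 21% is a ceiling and not an estimate; it does not remove the gap from the text.

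The consequence is also limited. A reader might infer that an opacity from Part A would be counted as a Part B result and distort the primary safety analysis. The documents do not support that. Section 12.3.4.6 presents eye findings as a listing only, so no planned summary of them changes, and the opacity would still be recorded after LUM/IVA exposure in the same child. What is lost is its timing within the study. If the investigator reported it as an adverse event, the part-by-part definition in Section 12.3.4.1 could place it among Part B treatment-emergent events, but that depends on the report and its start date. Section 8.3.3 also regards the animal finding as unlikely to be relevant to humans, and Part A dosing lasts only 15 days.

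A reader might further infer that criterion 9 and Section 11.6.6 contradict each other, since the first mentions any history of opacity and the second a clinically significant one. They do not. Criterion 9 has two limbs, and Section 11.6.6 restates the second without saying that only significant opacities exclude. Nor does any text say that a non-significant finding at one screening becomes history at the next. At most this is an ambiguity, and it forms no part of this point.

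**Conclusion.** The point holds as a gap in the waiver. Followed as written, the protocol can clear a child for Part B on a lens examination from before Part A dosing, and the 30-day gap in criterion 7 does not prevent it at nominal timing.

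At most about 12 children could be affected, and possibly none. The result assumes that the Part A examination was done within the Part A screening window, that 30 days is the longer limb of criterion 7, and that Part B screening opens for the child before the waiver lapses. No numerical estimate in the planned analysis changes. What is affected is eligibility under criterion 9 and the ability to say in which part an opacity arose. This is a minor point, worth acting on because the assessment is named in the Part B primary safety endpoint and the correction costs almost nothing.

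**What to change.** Add one sentence to criterion 9, the Table 3-3 footnote and Section 11.6.6: for subjects who received LUM/IVA in Part A, the examination used for Part B screening must be dated after the last Part A dose. The rescreening exemption in Section 8.1.5 should be read with the same condition. The exemption for documented bilateral lens removal is unaffected.

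The cost is that a few children, at most about 12, lose the waiver and have a dilated slit-lamp examination at age 2 to 5. Table 3-3 already schedules that examination, and Section 8.1.6 already allows an extra week of screening to arrange it.

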9.3 Study Restrictions

Part A

Prohibited medications and certain foods are not allowed during the time periods summarized in Table 9-1.

A nonexhaustive list of study prohibitions and cautions for food and medication will be provided in the study reference manual.

Table 9-1 Study Restrictions – Part A

	Study Period	
Restricted Medication/Food ^a	Screening Period	Treatment Period
Moderate and strong CYP3A inhibitors and inducers	None allowed within 14 days before the first dose of LUM/IVA	None allowed until after the Safety Follow-up Visit
Grapefruit/grapefruit juice, pomelos, star fruit, Seville oranges	None allowed within 14 days before the first dose of LUM/IVA	None allowed until last PK sample is taken

CYP: cytochrome P450; IVA: ivacaftor; LUM: lumacaftor; PK: pharmacokinetics

Note: The use of restricted medication in subjects with a medical need will be addressed on a case-by-case basis with the medical monitor or authorized designee.

^a See Section 9.4 for guidance for concomitant medications.

Part B

Prohibited medications and certain foods are not allowed (Screening Period through Week 24 of Part B) as summarized in Table 9-2.

A nonexhaustive list of study prohibitions and cautions for food and medication will be provided in the study reference manual.

Table 9-2 Study Restrictions – Part B

	Study	Period
Restricted Medication/Food ^a	Screening Period	Treatment Period
Strong CYP3A inducers	None allowed within 14 days before the first dose of LUM/IVA	None allowed
Strong CYP3A inhibitors	None allowed within 14 days before the first dose of LUM/IVA	Use with caution

CYP: cytochrome P450; IVA: ivacaftor; LUM: lumacaftor

Note: The use of restricted medication in subjects with a medical need will be addressed on a case-by-case basis with the medical monitor or authorized designee.

9.4 Prior and Concomitant Medications

9.4.1 Prohibited Medications

Part A and Part B

The prohibited medications that are described for Part A and Part B in Section 9.3 are not allowed in this study while subjects are receiving LUM/IVA.

The use of CYP3A substrates is not prohibited in this study, but investigators need to be aware that LUM appears to be a strong inducer of this CYP isoenzyme. Therefore, the efficacy of drugs extensively metabolized by this isoenzyme may be affected. Each investigator should evaluate the benefit/risk ratio of using such drugs with LUM during this study. Investigators should discuss any concerns regarding the use of CYP3A substrates during this study with the Vertex medical monitor or authorized designee.

The use of CYP2C and 2B6 substrates are not prohibited in this study, but investigators need to be aware that LUM has been shown in vitro to induce CYP2B6, CYP2C8, CYP2C9, and CYP2C19; inhibition of CYP2C8 and CYP2C9 has also been observed in vitro. Additionally, in vitro studies suggest that IVA may inhibit CYP2C9. Therefore, concomitant use of LUM/IVA with CYP2B6, CYP2C8, CYP2C9, and CYP2C19 substrates may alter the exposure of these substrates.

Each investigator should evaluate the benefit-risk ratio of using such drugs with LUM and IVA during this study and discuss the use of these substrates during this study with the medical monitor or authorized designee.

A nonexhaustive list of study prohibitions and cautions for food and medications will be provided in the study reference manual.

^a See Section 9.4 for guidance for concomitant medications.

